4.4 STUDY DURATION

For each subject, the study is expected to last up to 8 days: one day of dosing, 7 days of follow-up, and a window of up to 42 days to complete the screening procedures.

4.5 END OF STUDY DEFINITION

A subject is considered to have completed the study if he or she has completed the study, including the last visit or the last scheduled procedure shown in the SoA, Section 1.3.

The end of the study is defined as completion of the last visit or procedure shown in the SoA in the study globally.

5 STUDY POPULATION

5.1 INCLUSION CRITERIA

Subjects are eligible to be included in the study only if they meet the criteria relevant to their disease status:

Type of Subject and Disease Characteristics

Subjects with Parkinson's Disease

1. Clinically established Parkinson's disease based on Movement Disorder Society (MDS) Clinical Diagnostic Criteria for Parkinson's disease (Table 9) and a modified Hoehn & Yahr scale of 1-3 (Table 10).
2. No suspected atypical parkinsonian syndromes due to drugs, metabolic disorders, encephalitis, or degenerative diseases.

Subjects with ALS

3. Confirmed diagnosis of ALS with both upper and lower motor neuron involvement (Table 11).

Subjects with MSA

4. Diagnosis of clinically established MSA according to MDS 2022 Criteria (Wenning, 2022); refer to Appendix 4, Section 10.4.2.

Age, Gender, Informed Consent, Pregnancy and Contraception

5. Male and female subjects 18 years and older at the time of signing the informed consent.
6. Ability to undergo retinal imaging.
7. Subject or legally authorized representative must provide signed informed consent (or signed assent form) prior to study entry and have the ability and willingness to attend and comply with the necessary study procedures and visits at the study site. For subjects unable to physically sign the informed consent, a guardian or trusted care giver can sign on their behalf in presence of an independent witness.

Contraception

8. Contraception use by study subjects of childbearing potential (male and female) and female partners of childrearing potential male subjects should be consistent with local regulations regarding the methods of contraception for those participating in clinical studies. For details, refer to Section 10.2.
9. Female subjects of childbearing potential and female partners of childbearing potential male subjects must refrain from oocyte donation for up to 30 days after study drug administration.

10. Male subjects must refrain from sperm donation for 90 days after study drug administration.
11. Females of childbearing potential must have a negative serum pregnancy test at Screening and a negative urine pregnancy test on Day 1 (predose). Females not of childbearing potential must be surgically infertile or postmenopausal (defined as cessation of regular menstrual periods for at least 12 months) at Screening.

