1.3 SCHEDULE OF ACTIVITIES (SoA)

Table 1 Schedule of Activities (Subjects with Neurodegenerative Diseases, All Dose Cohorts)

Study Procedures	Screening ¹	Treatment	Follow-up	Notes
Study Visit	-42 to -1	Day 1	Day 8/EOS/ET	
Visit window (days)	42		+2	
Informed consent	X			
Domiciled		X ^a		a. Subjects will be admitted to the clinical research unit in the morning for 8 hours confinement
Medical/ocular history/Physical exam	X			On Day 1, PE may be repeated if abnormalities are detected at screening. Relevant ocular and disease-specific history will be captured up to date of diagnosis.
Eligibility (inclusion/exclusion criteria)	X			
Body weight and Height	X			
Eye examination/	X	X	X	Refer to Section 8.1.1.
Color fundus photography	X			
Vital signs	X	X ^b	X	b. To be collected predose, and at 0.25, 0.5, 1, 2, 8 hours postdose. A window of \pm 5 minutes will be allowed for measurements up to 2 hours, and \pm 10 minutes beyond 2 hours.
12-lead safety (ECG)	X	X ^c	X	c. Triplicate at the following timepoints: predose (within 1 hour), and at 90 minutes (\pm 15 minutes) and 8 hours (\pm 60 minutes) postdose or before discharge
Safety laboratories	X	X ^d	X	Refer to Section 10.2. d. To be collected predose on Day 1 and before discharge
Urinalysis	X	X	X	
Pregnancy test	S	U (predose)	U	S = Serum; U = Urine
Adverse event reporting	X	X	X	

Study Procedures	Screening ¹	Treatment	Follow-up	Notes
Study Visit	-42 to -1	Day 1	Day 8/EOS/ET	
Visit window (days)	42		+2	
Concomitant medications	X	X	X	
Retinal fundus fluorescence (FF) imaging		X ^e	X	e. Refer to Section 8.1.2
Retinal optical coherence tomography (OCT) and OCT angiography (OCTA)	X		X	
Blood PK sampling		X ^f		f. On Day 1, PK blood samples will be collected at the following time points: 0 (predose), and at 3, 6, 15, and 30 minutes postdose and 1, 2, 4, 6, and 8 hours postdose. A window of ± 5 minutes will be allowed for samples collected from 30 minutes to 2 hours, and ± 10 minutes beyond 2 hours.
Study drug administration		X		

Abbreviations: AE, adverse events; ECG, electrocardiogram; EOS, end of study; ET, early termination; FU, follow-up; PE, physical examination; PK, pharmacokinetics.

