All cohorts will include subjects with neurodegenerative diseases (Parkinson's disease, MSA and/or ALS). The decision to escalate to the next dose level will be made based on review of all available safety and tolerability data collected, including AEs, ECGs, vital signs, and laboratory safety results of the previous dose levels after single dose administration in at least 3 subjects from each cohort. Based on emerging data, additional cohort(s) and/or an intermediary dose may be investigated with prior approval by the SMC. The study may progress to the next cohort if approved upon satisfactory review of available safety data of the previous cohort(s) by the SMC. During each safety review, the SMC will make a decision to either continue enrollment to the next planned cohort, add additional subjects to the current cohort, or change the dose of the next cohort.

Enrollment into each cohort will begin with 1 sentinel subject who will be observed for at least 8 hours at the clinic and evaluated by the investigator at 24 hours following dosing by the investigator. If no safety issues are observed, the remaining subjects will be enrolled into that cohort. Dosing of remaining subjects at the same center will be staggered by at least 1 hour. Dosing within a cohort will continue unless stopping rules are met.

For all dose cohorts, after signing the informed consent, subjects will be screened. If needed, the screening procedures may occur over a period of up to 42 days prior to dosing. On Day 1, subjects will be admitted to the clinical research unit for 8 hours confinement. Eye examination and retinal imaging will be conducted before administration of the study drug. AMDX-2011P will be administered through a single IV bolus injection followed by repeated retinal imaging and PK and safety assessments as outlined in the Schedule of Activities (SoA; Section 1.3). On Day 8 (end of study), there will be a follow-up visit for retinal imaging and safety assessments.

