10.3 CONTRACEPTIVE GUIDANCE AND COLLECTION OF PREGNANCY INFORMATION

10.3.1 Definitions

Woman of Childbearing Potential (WOCBP)

A woman is considered fertile following menarche and until becoming postmenopausal unless permanently sterile (see below).

If fertility is unclear (e.g., amenorrhea in adolescents or athletes) and a menstrual cycle cannot be confirmed before first dose of study drug, additional evaluation should be considered.

Women in the following categories are not considered WOCBP

1. Premenarchal
2. Premenopausal female with 1 of the following:
 - Documented hysterectomy
 - Documented bilateral salpingectomy
 - Documented bilateral oophorectomy

For individuals with permanent infertility due to an alternate medical cause other than the above, (e.g., mullerian agenesis, androgen insensitivity), investigator discretion should be applied to determining study entry.

Note: Documentation can come from the site personnel's review of the subject's medical records, medical examination, or medical history interview.

Postmenopausal female

- A postmenopausal state is defined as no menses for 12 months without an alternative medical cause.
 - A high follicle stimulating hormone (FSH) level in the postmenopausal range may be used to confirm a postmenopausal state in women not using hormonal contraception or hormonal replacement therapy (HRT). However, in the absence of 12 months of amenorrhea, confirmation with more than one FSH measurement is required.
- Females on HRT and whose menopausal status is in doubt will be required to use one of the non-estrogen hormonal highly effective contraception methods if they wish to continue their HRT during the study. Otherwise, they must discontinue HRT to allow confirmation of postmenopausal status before study enrollment.

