10.3.2 Contraception Guidance

Male Subjects

Male subjects are eligible to participate if they agree to the following from informed consent through 90 days after study drug administration:

- Refrain from donating sperm, except for the purpose of fertility analysis as part of this protocol
PLUS, either:
- Be abstinent from heterosexual intercourse as their preferred and usual lifestyle (abstinent on a long term and persistent basis) and agree to remain abstinent

OR

- Must agree to use double barrier contraception (a male condom with spermicide)

Female Subjects

- A female subject is eligible to participate if she is not pregnant or breastfeeding, and at least one of the following conditions applies:
 - Is not a woman of childbearing potential (WOCBP)

OR

- Is a WOCBP and using a contraceptive method that is highly effective (with a failure rate of < 1% per year), preferably with low user dependency (see table below), from consent through 30 days after study drug administration, and agrees not to donate eggs (ova, oocytes) for the purpose of reproduction during this period. The investigator should evaluate the effectiveness of the contraceptive method in relationship to the first dose of study drug.
- A WOCBP must have negative serum pregnancy test (minimum sensitivity 25 IU/L or equivalent units of human chorionic gonadotropin [HCG]) within 72 hours prior to receiving the first administration of study drug and a negative urine pregnancy test before first administration of study drug. If the urine test is positive or cannot be confirmed as negative, a serum pregnancy test is required and results must be negative.

Contraceptive use by men or women should be consistent with local regulations regarding the use of contraceptive methods for those participating in clinical studies.

Highly Effective Methods^a That Have Low User Dependency	

 Implantable progestogen-only hormone contraception associated with inhibition of ovulation^b Intrauterine device (IUD) (hormonal and non-hormonal) Surgical sterilization Bilateral tubal occlusion or ligation Vasectomized partner 	(Vasectomized partner is a highly effective contraceptive method provided that the partner is the sole sexual partner of the woman of childbearing potential and the absence of sperm has been confirmed. If not, an additional highly effective method of contraception should be used. Spermatogenesis cycle is approximately 90 days.)

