6.4 Demographics and Baseline Characteristics

Demographic and baseline characteristics will be summarized for each cohort and overall, including age (years), sex (male, female), child-bearing potential? (Yes, No: bilateral oophorectomy, bilateral tubal ligation, hysterectomy, post-menopausal, and other), contraception (Yes, No), ethnicity (Hispanic or

Latino, Not Hispanic or Latino), Race (American Indian or Alaska Native, Asian, Black or African American, Native Hawaiian or Other Pacific Islander, White, Other), height (inches), weight (lbs), and iris color (Blue, Green, Brown, Black, Grey, Hazel, Other).

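### Inclusion criterion 11 and Table 1 conflict with Section 10.3 on when the serum pregnancy test is due and on who counts as of childbearing potential

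*Protocol*

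**What the plan says.** **Serum test timing.** Protocol Section 5.1, criterion 11, states "Females of childbearing potential must have a negative serum pregnancy test at Screening and a negative urine pregnancy test on Day 1 (predose". Table 1 (Section 1.3) places a serum test at Screening and urine tests on Day 1 before dosing and at follow-up, under the key "S = Serum; U = Urine". Screening is long: Section 4.1 says that "the screening procedures may occur over a period of up to 42 days prior to dosing". Section 10.3.2 requires that a woman of childbearing potential have a negative serum test "within 72 hours prior to receiving the first administration of study drug and a negative urine pregnancy test before first administration of study drug".

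**Classification.** Criterion 11 states "Females not of childbearing potential must be surgically infertile or postmenopausal (defined as cessation of regular menstrual periods for at least 12 months". It does not say which operations make a woman surgically infertile. Section 10.3.1 lists three documented operations (hysterectomy, bilateral salpingectomy, bilateral oophorectomy) and otherwise says "A postmenopausal state is defined as no menses for 12 months without an alternative medical cause". It adds an FSH route, under which "in the absence of 12 months of amenorrhea, confirmation with more than one FSH measurement is required", and a rule for women on HRT whose status is in doubt.

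**Tubal ligation.** Section 10.3.1 does not list it among the operations. Section 10.3.2 lists it as a highly effective contraceptive method. SAP Section 6.4, in the demographics summary, puts it among the reasons for not being of childbearing potential: "bilateral oophorectomy, bilateral tubal ligation, hysterectomy, post-menopausal, and other".

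**Who is tested.** Criterion 11 requires tests only of women of childbearing potential, and Table 8 (Section 10.2) ties the hCG test to the same group.

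**Cross-references.** Inclusion criterion 8 sends the reader to Section 10.2, the laboratory tests, for contraception details. Section 8.4.8 also cites Section 10.2 for the collection of pregnancy details.

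**The concern.** Both texts are worded as conditions of eligibility, and Section 8 allows no waivers or exemptions. A site that follows criterion 11 and Table 1 to the letter can still enroll a woman whom Section 10.3.2 makes ineligible, because her serum test is too old. This is an eligibility question and a source of protocol deviations.

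The classification difference matters more for exposure. Being classed as not of childbearing potential takes a woman out of required pregnancy testing and out of the contraception requirement, so for her the Day 1 urine test is not a required backstop. If Section 10.3.1 would class the same woman as of childbearing potential, the two texts disagree on whether she is protected at all.

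Section 2.3.1 describes a first-in-human study. Table 2 lists mutagenicity as a potential risk and keeps healthy volunteers out of clinical studies until more is known. The signal there is limited: bacterial, only with metabolic activation, and with no chromosomal aberrations in mammalian cells.

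**Working it through.** No sample size, power or error rate is involved, and the plan gives no figure to reproduce. The check is a day count and a side-by-side reading.

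**Day count for the serum test**

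- Input 1: Screening runs from Day -42 to Day -1 (Table 1), which is 42 days.
- Input 2: the Section 10.3.2 limit is 72 hours, which is 72 / 24 = 3 days.
- Assumption: there is no Day 0, so Day -1 is the day before dosing. The 72 hours then reach back to Day -3, and at most Days -3, -2 and -1 qualify.
- Days that meet criterion 11 but not Section 10.3.2: 42 - 3 = 39, and 39 / 42 = 0.93.
- Sensitivity: if the calendar has a Day 0, only Days -2 and -1 of Screening qualify, and the share is 40 / 42 = 0.95.

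The two windows overlap in the last three (or two) days, so one test placed there satisfies both texts.

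**The same woman under each text**

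| Woman | Criterion 11 and Table 1 | Section 10.3 |
|---|---|---|
| A. 12 months of amenorrhea with another medical cause, not permanently infertile | Meets the stated definition of postmenopausal; no test required | Not postmenopausal; of childbearing potential, so needs contraception, a serum test within 72 hours and a predose urine test |
| B. Bilateral tubal ligation | Depends on the undefined term for surgical infertility; if ligation counts, no test required | Not among the listed operations, so of childbearing potential; the ligation itself satisfies the contraception rule, but both tests are still due |
| C. Under 12 months of amenorrhea, repeated FSH in the postmenopausal range, no hormonal treatment | Does not meet the definition | Can be confirmed as postmenopausal |
| D. Of childbearing potential, negative serum test on Day -20, negative predose urine test | Satisfied | Not satisfied: serum test too early |
| E. Of childbearing potential, negative serum test on Day -2, negative predose urine test | Satisfied | Satisfied |

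Cases A and C show that the definitions differ in both directions, so neither is simply a summary of the other. Case A is the clearest, because it needs no interpretation of the surgical term and because contraception as well as testing is at issue. Cases D and E show that the timing conflict depends on when in Screening the test is taken.

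**The case against.** The strongest reply is that Section 10.3 supplies the detail behind criterion 11. It is listed in the contents, directly follows Section 10.2, is cited correctly in Section 7.1.1, and is itself phrased as eligibility. A careful site could apply both texts together and satisfy both with one late serum test. That is possible, but criterion 11 does not cite Section 10.3, criterion 8 points elsewhere, and Table 1 does not schedule a test to meet the 72-hour rule. Case C also cannot be resolved by calling one text the detail of the other.

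Other safeguards stand. Women classed as of childbearing potential need a negative urine test before dosing under both texts. Section 10.3.2 adds a serum test if the urine result is positive or unclear. Exclusion criterion 9 bars any pregnant woman, and Section 10.2 lets the investigator order additional tests. Table 1 does not itself limit testing to women of childbearing potential; that limit comes from criterion 11 and Table 8.

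Several stronger inferences are tempting and are not supported:

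- *Most screening serum tests would breach Section 10.3.2.* The 93% counts calendar days. The documents do not say when in Screening tests are done.
- *The timing conflict leaves women untested on the day of dosing.* It does not, because of the predose urine test.
- *Criterion 11 lets a woman who still bleeds irregularly count as postmenopausal.* This isolates the word regular from the term being defined. The reading is strained, and the point does not need it. Case A is firmer: the criterion's own definition says nothing about cause, while Section 10.3.1 does.
- *A woman with a tubal ligation escapes contraception.* Section 10.3.2 accepts ligation as contraception; only her tests differ.
- *The SAP decides eligibility.* Section 6.4 is a list of demographic categories, and the SAP also covers a second sub-study under another protocol.
- *No disease brings a lower age limit above 18.* The MSA criteria in Section 10.4.2 require onset after age 30.

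**Conclusion.** The conflict is real in the current text on both points. On timing, about 39 of 42 permitted days satisfy criterion 11 and Table 1 but not Section 10.3.2, assuming no Day 0. For women classed as of childbearing potential this is mainly an eligibility and deviation problem. On classification, the texts can place the same woman on opposite sides, and that placement decides whether she must be tested. Tubal ligation is handled inconsistently between Section 10.3 and SAP Section 6.4, a smaller matter of coding.

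The number of women affected is not given. It is likely to be small, given the diseases studied, but with a minimum age of 18 it need not be zero. Nothing here touches the sample size, an error rate or the planned analyses. The point should be corrected because the drug is first-in-human with a listed mutagenicity risk and the correction is cheap. It does not show that a pregnant woman would be dosed.

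**What to change.** Reconcile Table 1 (Section 1.3), criterion 11 (Section 5.1) and Sections 10.3.1 and 10.3.2, so that one definition of childbearing potential and one serum-test window apply throughout and Table 1 schedules the test to match. Say which operations the surgical term covers. Align the tubal ligation category in SAP Section 6.4 with the definition kept. Correct the references to Section 10.2 in criterion 8 and Section 8.4.8. The sponsor's clinical team decides which definition and window stand; this review takes no view on that.

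The cost is protocol and SAP wording and, depending on the window chosen, at most a retimed serum test for the few women of childbearing potential who are screened early.

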5.2 EXCLUSION CRITERIA

Subject meeting ANY of the following exclusion criteria are NOT eligible to be enrolled into the study:

Medical Conditions

1. Presence of any underlying physical or psychological medical condition that, in the opinion of the investigator, would make it unlikely that the subject will complete the study per protocol.
2. Clinically significant laboratory abnormalities assessed by the investigator.
3. Active malignancy and/or history of malignancy in the past 5 years, with the exception of completely excised non-melanoma skin cancer or low-grade cervical intraepithelial neoplasia.
4. Prolonged QTcF (>450 ms for males and >470 ms for females), cardiac arrhythmia, or any clinically significant abnormality in the resting ECG, as judged by the investigator.
5. Presence of any ocular condition that, in the opinion of the investigator, would significantly hinder the ability to detect and quantify hyper-fluorescent puncta (e.g., eyes with significant hyper-autofluorescence that would mask the ability to detect, quantify, and discern post-injection hyper-fluorescent signal from pre-injection hyper-autofluorescence signal). These conditions may include, but are not limited to; age-related macular degeneration, central serous chorioretinopathy, diabetic retinopathy, macular dystrophies such as Stargardt disease, retinitis pigmentosa, choroideremia, white dot syndromes, and drug toxicities such as hydroxychloroquine toxicity.

Prior/Concomitant Prohibited Therapy

6. Use of any new prescription therapies or vaccines within 7 days prior to the study drug administration.
7. Drugs with potential phototoxicity per Package Insert are prohibited within 48 hours or 5 half-lives, whichever is longer, prior to first study drug until End-of-study (EOS) visit, except for those required for treatment of underlying disease. Examples of such drugs include the following: Chloroquine (Aralen), hydroxychloroquine (Plaquenil), Thioridazine (Mellaril), Topiramate (Topamax), vemurafenib, voriconazole,

doxycycline, hydrochlorothiazide, amiodarone, furosemide, allopurinol, phenothiazine, and chlorpromazine.

Prior/Concurrent Clinical Study Experience

8. Administration of investigational product in another study within 30 days prior to the first study drug administration, or five half-lives, whichever is longer.

Other Exclusions

9. Females who are pregnant or breastfeeding.

5.3 LIFESTYLE CONSIDERATIONS

Not applicable.

5.4 SCREEN FAILURES

Subjects will be assigned a subject number upon entry of data into the Electronic Data Capture (EDC) system.

Screen failures are defined as subjects who consent to participate in the clinical study but are not subsequently assigned to a cohort. A minimal set of screen failure information is required to ensure transparent reporting of screen failure subjects to meet the Consolidated Standards of Reporting Trials (CONSORT) publishing requirements and to respond to queries from regulatory authorities. Minimal information includes demography, screen failure details, eligibility criteria not met, and any SAE.

Potential candidates who do not meet the criteria for participation in this study (screen failure) may be rescreened.

